It is important to note that GnRH agonists are not considered teratogenic (23). In over 340 women exposed to GnRH agonists in the mid-luteal phase, the rate of birth defects and miscarriages (2.5% and 15%, respectively) was similar to the general IVF population (24-26).

There is a need for further research to examine the effectiveness of GnRH agonist treatment as luteal support in in NCs FET. Conducting a prospective randomized controlled study will allow to determine the treatment efficacy of GnRH agonist and HCG in relation to the standard luteal support with progesterone.

The aim of the study is to compare the pregnancy rate between women treated with GnRH agonist together with HCG and standard luteal support with progesterone in the return of frozen embryos in natural cycles and in vitro fertilization treatments.

Primary outcome

- Clinical pregnancy rate – visualization of intrauterine gestational sac on ultrasound divided by number of transfers

Secondary outcomes

- Overall pregnancy rate - number positive bhCG divided by total number of transfers
- Ongoing pregnancy rate – visualization of fetal cardiac activity divided by total number of transfers
- Implantation rate – number of gestational sacs divided by number of embryos transferred
- Ectopic pregnancy rate – number of ectopic pregnancy divided by number of positive bhCG
- Miscarriage rate – number of non-viable before 24 weeks divided by total number of positive bhCG
- Live birth rate – number of live births after 24 weeks divided by number of transfers.

Study methods

Women who undergo natural cycle FET at the IVF center in Shaare Zedek Medical Center will be recruited.

During the visit to the clinic, the women's demographic and clinical data will be collected. The women who are found to be suitable according to the research criteria will receive an explanation of the nature of the study and will sign a consent form for participation in the study in accordance with the procedures of the Institutional Helsinki Committee.

The women can give an agreement until the ET day.

The number of embryos that will be returned will be determined according to the age of the woman, the number of treatment cycles and the quality of the embryos in accordance with the accepted policy in the unit.

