The distribution of the patients to the two study groups will be done randomly by computer in a ratio of 1:1. Sealed envelopes containing information regarding the type of treatment for luteal support will be attached to the consent forms.

144 women will be divided into two groups, and each group will receive a different luteal treatment:

Study group – patients will receive luteal support of GNRH agonist and HCG according to departmental protocol:

Cleavage stage embryo:

- ET day (embryo day 2-3) - Ovitrelle 125mcg
- Day 3 after ET - Ovitrelle 125mcg + Decapeptyl 0.1mg
- Day 6 after ET - Ovitrelle 125mcg
- Day 9 after ET - Ovitrelle 125mcg

Embryo blastocyst stage:

- ET day (embryo day 5-6) - Ovitrelle 125mcg + Decapeptyl 0.1mg
- Day 3 after ET - Ovitrelle 125mcg
- Day 6 after ET - Ovitrelle 125mcg

Control group - patients will receive luteal support of vaginal progesterone – 100 mg Endometrin twice daily until week 8 of pregnancy.

Clinical pregnancy will be defined as the demonstration of an intrauterine gestational sac. Other pregnancy outcomes will be received in a telephone conversation with the patients and computer database nine months after the treatment.

Statistical calculations

Based on the clinical pregnancy rate in the prospective study by Bjuresten, et al [13], where a clinical pregnancy rate of 32% was found among women treated with progesterone for luteal support, and given an alpha of 5% and a power of 80%, 144 women (72 women in each group) are required in order to demonstrate a clinical pregnancy rate of 55% in the study group.

Comparison of categorical variables will be carried out using the CHI-SQUARE TEST. Comparison of continuous variables will be performed using the Students t-Test or Mann–Whitney U method depending on the variable distribution (normal vs. non-normal distribution, respectively). A multivariate regression will also be conducted in order to determine which variables are significantly and independently related. Statistical significance will be defined when P values are less than 0.05

Inclusion Criteria

- Normo-ovulatory women
- Women undergoing frozen embryos transfer in a natural cycle
- Age 18-45
- BMI 18-35

Exclusion Criteria

- Women undergoing medicated frozen embryos transfer
- Women with a BMI over 35 or under 18.
- Women with hydrosalpings

- Women with defects or uterine malformations (congenital) or acquired such as myomas

- Egg donation and surrogacy

- Use of preimplantation genetic testing

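### The miscarriage rate does not say which losses count, and its positive-bhCG denominator could be disturbed by injected hCG in the study arm only

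*Combined protocol and SAP*

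**What the plan says.** All locations are in the combined protocol and SAP.

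- **Secondary outcomes, miscarriage rate:** "number of non-viable before 24 weeks divided by total number of positive bhCG". No noun follows the adjective. No prior gestational sac is required, and neither biochemical nor ectopic losses are excluded.
- **Secondary outcomes, ectopic pregnancy rate:** "number of ectopic pregnancy divided by number of positive bhCG", which has the same denominator.
- **Secondary outcomes, overall pregnancy rate:** "number positive bhCG divided by total number of transfers". This is where the denominator comes from. No test day or positivity threshold is given, and biochemical pregnancy is not mentioned anywhere.
- **Study methods, clinical pregnancy:** "Clinical pregnancy will be defined as the demonstration of an intrauterine gestational sac". The miscarriage rate is not tied to this definition.
- **Study methods, study group:** "patients will receive luteal support of GNRH agonist and HCG according to departmental protocol". The last hCG entry in the cleavage-stage schedule is "Day 9 after ET - Ovitrelle 125mcg"; in the blastocyst schedule it is "Day 6 after ET - Ovitrelle 125mcg".
- **Study methods, control group:** "patients will receive luteal support of vaginal progesterone". No hCG is listed.
- **Study methods, follow-up:** pregnancy outcomes other than clinical pregnancy are obtained by telephone and from the computer database nine months after treatment.

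**The concern.** Two things are unsettled.

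First, the numerator can be read broadly (every positive test that is not a viable pregnancy by 24 weeks) or narrowly (only losses of an established intrauterine pregnancy). The broad reading is the literal one. It mixes biochemical loss, ectopic pregnancy and clinical miscarriage, and it places an ectopic in two listed outcomes. The choice would be made after nine-month outcomes are in hand, and no blinding is described.

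Second, the denominator is all positive bhCG tests, while hCG is injected in one arm only. A positive test caused by residual injected hCG could not arise in the progesterone arm. Such a test enters the denominator on either reading, and on the broad reading it enters the numerator as well. Miscarriage is an outcome that readers will take as evidence of harm or benefit of the new regimen, so a distortion confined to one arm matters even for a secondary outcome.

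**Working it through.** **The plan's own figure.** The documents give no expected miscarriage rate. The figure that can be checked is the sample size (Statistical calculations: 32% versus 55%, alpha 5%, power 80%). With a two-sided test, pooled variance and no continuity correction:

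n = [1.960 × √(2 × 0.435 × 0.565) + 0.842 × √(0.32 × 0.68 + 0.55 × 0.45)]² / 0.23² = 71.7, so 72 per arm and 144 in total. This reproduces the plan, and nothing below changes it.

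**Inputs for the illustration.**
- Clinical pregnancies per 72 women: 0.32 × 72 = 23.04, taken as 23 (control rate); 0.55 × 72 = 39.6 (planned study rate).
- Clinical loss m = 15% of clinical pregnancies. The background text cites 15% for miscarriage but does not give its denominator, so its use here is an assumption.
- b = share of true positive tests that never show an intrauterine sac (biochemical or ectopic): 10%, 20% or 30%. Assumed; the documents give no figure.
- f = study-arm positives due only to residual injected hCG: 2, 4 or 6 of 72. Assumed; the documents give no figure.

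**Step 1: effect of the wording alone (f = 0).**
- Broad reading: b + (1 − b)m
- Narrow numerator over positive bhCG: (1 − b)m
- Per clinical pregnancy: m

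| b | Broad | Narrow over positives | Per clinical pregnancy |
|---|---|---|---|
| 10% | 0.10 + 0.135 = 23.5% | 13.5% | 15% |
| 20% | 0.20 + 0.120 = 32.0% | 12.0% | 15% |
| 30% | 0.30 + 0.105 = 40.5% | 10.5% | 15% |

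The clinical pregnancy rate cancels out. With the same b and m in both arms, the wording alone gives the same rate in each arm, whether clinical pregnancy is 32% or 55%.

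**Step 2: the share due to ectopics.** Taking ectopics out of the broad numerator lowers the rate by exactly their share of positives. If that share is 1-3% (assumed), the effect is 1-3 percentage points. Biochemical losses account for the rest of the gap.

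**Step 3: residual-hCG positives in the study arm, at b = 20%.**
- At 32%: positives = 23 / 0.8 = 28.75; without a sac 5.75; clinical losses 0.15 × 23 = 3.45; broad numerator 9.20.
- At 55%: positives = 39.6 / 0.8 = 49.5; without a sac 9.9; clinical losses 0.15 × 39.6 = 5.94; broad numerator 15.84.
- Broad rate = (numerator + f) / (positives + f). Narrow rate = clinical losses / (positives + f).

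| f | Broad, 32% | Broad, 55% | Narrow, 32% | Narrow, 55% |
|---|---|---|---|---|
| 0 | 9.20/28.75 = 32.0% | 15.84/49.5 = 32.0% | 12.0% | 12.0% |
| 2 | 11.20/30.75 = 36.4% | 17.84/51.5 = 34.6% | 11.2% | 11.5% |
| 4 | 13.20/32.75 = 40.3% | 19.84/53.5 = 37.1% | 10.5% | 11.1% |
| 6 | 15.20/34.75 = 43.7% | 21.84/55.5 = 39.4% | 9.9% | 10.7% |

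No true loss has been added in any row. The rate per clinical pregnancy stays at 15% throughout, because a residual-hCG positive never has a sac.

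**The case against.** The case on the other side has four parts.

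- **The label settles the numerator.** The item is called a miscarriage rate and sits beside a separate ectopic outcome, so a sensible team would count miscarriages only. This stands in part: the broad reading is the literal one but not the only one, and the defect is an incomplete definition. It does not rescue the rate, because on the narrow reading the denominator still contains any residual-hCG positives.
- **Ectopics are not double counted.** A reader might infer that an ectopic is counted twice within one rate. It is not. On the broad reading it appears once in each of two outcomes, the plan never adds the two, and the likely effect is small.
- **The wording is the same in both arms.** A reader might infer that the rate is inflated unequally between arms. The documents do not support this as a fact. Step 1 gives identical rates; an imbalance needs residual-hCG positives, whose frequency is unknown, and its direction reverses with the reading. What stands is that a route to imbalance exists in one arm only and nothing in the plan closes it.
- **A stated bhCG test day and threshold might be enough.** If they removed residual-hCG positives, the difference between arms from this source would go. The unclear status of biochemical and ectopic losses would remain.

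It is also fair that no decision rule rests on this rate.

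**Conclusion.** The concern holds as an incompletely defined secondary outcome whose denominator is exposed to a treatment effect on the test itself. On the assumptions shown, the unstated rule moves the rate between about 12% and 32% at b = 20%, against 15% per clinical pregnancy. Two to six residual-hCG positives would shift the study-arm rate up to about 36-44% (at 32% clinical pregnancy) or 35-39% (at the planned 55%) on the broad reading, and down to about 10-11% on the narrow reading at either rate.

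These are illustrations. The shares without a sac and the number of false positives are assumed, and the documents do not allow either to be estimated. The plan does not establish that the study regimen will appear to raise miscarriage; it leaves the comparison open to distortion in either direction. The definition should be settled before outcomes are tabulated.

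**What to change.** Define miscarriage as loss before 24 weeks of a pregnancy with a documented intrauterine gestational sac, divided by clinical pregnancies, and also report it per woman randomised. Both are needed. The first compares only women who became pregnant. The second keeps the randomised comparison but rises with the pregnancy rate: at 15% loss, 3.45/72 = 4.8% at 32% clinical pregnancy against 5.94/72 = 8.3% at 55%.

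Report biochemical loss (positive bhCG, no sac, not ectopic) and ectopic pregnancy as separate categories. Add a category for other or unknown outcome, for example termination, undetermined location or loss to follow-up. Classify per woman when more than one embryo is transferred. The outcomes that keep a positive bhCG in their definition remain exposed to residual hCG, so the plan should also state the test day and threshold it uses.

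The cost is a wording change to one secondary outcome. Positive bhCG, sac, ectopic and live birth are already needed for listed outcomes; termination and undetermined location are not named and would have to be recorded at follow-up. The denominator is smaller. For the same clinical losses at the control rate, the approximate 95% half-width is 1.96 × √(0.15 × 0.85 / 23) = 15 points, against 1.96 × √(0.12 × 0.88 / 28.75) = 12 points over all positives. The primary outcome and the sample size of 144 do not change.

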Endogenous progesterone secreted by the corpus luteum after natural ovulation is expected to provide an adequate luteal support as in spontaneous pregnancies. Therefore, it is assumed that there is no need for luteal support when embryos are transferred in NCs, and the benefit of medical luteal support is not conclusive (12-15). Nevertheless, a meta-analysis published in Human Reproduction in 2012, examined the effect of luteal support with progesterone and showed higher pregnancy rates in the group that received luteal support compared to those who did not receive it (16). It should be noted that most of the studies were performed with induction of ovulation by HCG.

Administration of HCG for luteal support is used both in fresh and frozen cycles. A previous study showed higher ongoing pregnancy rates in a group that received HCG within the day of natural LH surge together with vaginal progesterone from the day of embryo transfer compared to luteal support with progesterone alone. The use of 1500 units of HCG on cycle day 18 and 21 resulted with a significant increase in serum progesterone levels (17).

Administration of Gonadotropin Releasing Hormone (GnRH) analog as a treatment for luteal support in fresh IVF cycles has shown higher clinical pregnancy, multiple pregnancies, and live birth rates (18). When GnRH agonist is used (as single or repeated doses) it may cause an increase in LH secretion by the pituitary gland which augments the function of the corpus luteum and may lead to direct local stimulation of the endometrium [19].

In 2015, a retrospective cohort study from Israel compared the use of progesterone versus administration of HCG and GnRH agonist in NC FET. They showed a higher clinical pregnancy rate in the group treated with GnRH agonist and HCG (20). Another randomized prospective controlled showed that the addition of a GnRH agonist to luteal support with HCG compared with HCG alone in NC FET increased clinical pregnancy and implantation rates when frozen cleavage stage embryos were transferred (21). In 2016, a randomized prospective study from Finland examined the use of GnRH agonists in addition to standard vaginal progesterone support compared to a group treated with progesterone alone in 98 women undergoing NC FET (22). Both clinical and ongoing pregnancy rates were higher in the group treated

with GnRH agonists, but due to small sample size, the difference was not statistically significant.

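### Embryo stage fixes the study-group schedule but is named in neither the allocation nor the analysis; stratify by stage and carry it into the primary comparison

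*Combined protocol and SAP*

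**What the plan says.** The combined protocol and SAP, under Study methods, gives the study group a GnRH agonist with HCG on a schedule that depends on embryo stage.

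- Cleavage stage (embryo day 2-3 at transfer): HCG on the day of embryo transfer (ET) and on days 3, 6 and 9 after it. The agonist accompanies the second HCG dose: "Day 3 after ET - Ovitrelle 125mcg + Decapeptyl 0.1mg".
- Blastocyst stage: HCG on ET day and on days 3 and 6. The agonist accompanies the first HCG dose: "ET day (embryo day 5-6) - Ovitrelle 125mcg + Decapeptyl 0.1mg".

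The control group receives one vaginal progesterone regimen whatever the stage. On allocation the plan says "The distribution of the patients to the two study groups will be done randomly by computer in a ratio of 1:1", with sealed envelopes attached to the consent forms. No stratification factor is mentioned.

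Under Statistical calculations, the sample size rests on one rate per group and "144 women (72 women in each group) are required". Categorical variables are compared by chi-square test. A multivariate regression is also planned, but its outcome, covariates and any interaction are not listed. The stated aim is to compare agonist plus HCG with progesterone; comparing the two schedules is not an aim.

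**The concern.** Stage decides which schedule a study-group woman receives and how many HCG doses she is listed for: four (4 x 125 = 500 mcg) or three (3 x 125 = 375 mcg). It may also be related to the chance of pregnancy. A variable with both roles would normally appear in the allocation scheme, the primary analysis, or both. Here it appears in neither.

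The plan's background gives a further reason to record results by stage. The randomised trial it cites for adding an agonist to HCG in natural cycles is described as having "increased clinical pregnancy and implantation rates when frozen cleavage stage embryos were transferred".

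Two things are at stake. Chance may give the arms different stage mixes, and the named unadjusted test would carry that difference into the treatment effect. Any later look at results by stage would also be post hoc, with no agreed method or label.

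**Working it through.** **Inputs from the plan.** Control rate 32% ("where a clinical pregnancy rate of 32% was found among women treated with progesterone for luteal support"); the sample "are required in order to demonstrate a clinical pregnancy rate of 55% in the study group"; two-sided 5% alpha (sidedness is not stated, but two-sided reproduces the plan's figure) and 80% power; 72 women per group. The plan gives no stage mix and no pregnancy rate by stage, so both are assumed below.

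**1. The plan's sample size.** With a mean rate of 0.435:

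n = [1.96 x sqrt(2 x 0.435 x 0.565) + 0.8416 x sqrt(0.32 x 0.68 + 0.55 x 0.45)]² / 0.23² = (1.374 + 0.574)² / 0.0529 = 71.7, so 72 per group and 144 in total. This matches, and it applies to the pooled comparison.

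**2. The two schedules on a common clock.** Embryo age at transfer plus days after ET gives embryo age at each dose.

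| Embryo age (days) | Cleavage stage | Blastocyst stage |
|---|---|---|
| 2-3 | HCG (ET day) | none |
| 5-6 | HCG + agonist (day 3) | HCG + agonist (ET day) |
| 8-9 | HCG (day 6) | HCG (day 3) |
| 11-12 | HCG (day 9) | HCG (day 6) |

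The agonist falls at the same embryo age in both, and the last three HCG doses coincide. The difference is one earlier HCG dose at cleavage-stage transfer.

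**3. Chance imbalance in stage.** Assume 72 per arm, no stratification, and a blastocyst share p that is the same in expectation in both arms. Ten points of 72 is 7.2 women, so the counts must differ by at least 8. For two independent Binomial(72, p) counts, the exact probability is 21% at p = 0.5 and 17% at p = 0.3 or 0.7. A normal approximation gives 23% and 19%; it is higher because it ignores that counts are whole numbers.

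**4. Effect on the unadjusted estimate.** The SD of the between-arm difference in share is sqrt(2p(1-p)/72): 0.083 at p = 0.5 and 0.076 at p = 0.3. The 95% limits (1.96 x SD) are 16.3 and 15.0 points. If pregnancy rates differ between stages by 10 to 20 points (assumed), the shift at the limit runs from 0.150 x 10 = 1.5 points to 0.163 x 20 = 3.3 points.

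**5. Precision.** The 95% half-width is 1.96 x sqrt(0.2176/n + 0.2475/n), where 0.2176 = 0.32 x 0.68 and 0.2475 = 0.55 x 0.45.

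- Pooled, n = 72: ±15.8 points.
- One stage with n = 36 per arm: ±22.3 points.
- One stage with n = 22 per arm: ±28.5 points.

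**6. Power for a treatment-by-stage interaction.** Take an even mix, a 23-point effect in one stage and none in the other. SE = sqrt[(0.2176 + 0.2475 + 2 x 0.2176)/36] = 0.158. Power is approximately Phi(0.23/0.158 - 1.96) = Phi(-0.51) = 31%. Power for the 23-point difference within one stage is about 50% at 36 per arm and 33% at 22 per arm.

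**The case against.** The strongest reply is that the trial does not need stage. Its aim is agonist plus HCG against progesterone, the study arm follows a departmental protocol adapted to stage, and the pooled randomised comparison answers that aim. A shift of 1.5 to 3.3 points is small beside a pooled half-width of about 16 points, and it is chance error, not systematic bias. Imbalance also costs little within a stage: a 40 versus 32 split in place of 36 versus 36 widens the half-width only from 22.3 to 22.5 points (1.96 x sqrt(0.2475/32 + 0.2176/40)). The planned regression could include stage. All of this stands, and it keeps the point modest. It does not explain why a variable that fixes the regimen should be left out when including it is cheap, and an unlisted covariate is not a prespecified one.

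A reader might infer more: that the study arm is two separate regimens and the trial cannot show which one works. The documents do not support that. By embryo age the schedules largely align. Randomisation runs across both stages, so each stage has concurrent randomised controls, and a within-stage comparison is valid in expectation even without stratified lists. The limits are low power and no prespecification. Nor would stratified lists separate schedule from stage, because stage determines the schedule.

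A reader might also take the background to rest on cleavage-stage evidence alone. The cited cohort comparing HCG plus agonist with progesterone, and the randomised study adding an agonist to progesterone, are not described as limited to cleavage-stage transfers.

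**Conclusion.** The point holds as a gap in allocation and prespecification. It is not a flaw that invalidates the trial. The pooled comparison is valid for the stated aim. The avoidable cost is about a 17% to 21% chance of a stage imbalance of 10 points or more, and a shift of roughly 1.5 to 3.3 points in the unadjusted effect at the 95% imbalance limit. These figures assume simple allocation with 72 per arm, a blastocyst share of 30% to 70%, and a 10 to 20 point difference in pregnancy rate between stages; the last two are not in the documents.

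It would be wrong to expect stage-specific results to settle whether one schedule works. With interaction power near 31% at an even mix, even a 23-point effect in one stage and none in the other would usually go undetected. For the same reason, recommendations on a schedule should not be made to depend on its own stage stratum. No view is taken here on the doses or schedules.

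**What to change.** 1. **Allocation.** Generate two blocked 1:1 computer lists, one for planned cleavage-stage transfer and one for planned blastocyst transfer. Draw each woman's envelope from the list for her planned stage.
2. **Primary analysis.** Keep the pooled clinical pregnancy comparison as primary, but analyse it stratified by or adjusted for stage, for example with a Mantel-Haenszel risk difference and test. State this under Statistical calculations.
3. **Exploratory reporting.** Prespecify the study-minus-control difference with 95% CI within each stage, and a treatment-by-stage interaction. State that interaction power is low and that stage and schedule effects cannot be separated.

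The cost is a second envelope set, a sentence or two in the analysis section and one extra table, with no extra patients. The downside is that planned stage must be known before the envelope is opened. Envelopes are currently attached to consent forms, so they would have to be held separately or prepared by stage. This looks workable, since consent is allowed up to the ET day and study-group dosing starts that day. The stage-specific estimates will be imprecise (about ±22 points at 36 per arm) and should be labelled accordingly. If recruitment has already begun on a single list, items 2 and 3 can still be adopted before the data are compared by group.

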Prospective randomized control study of two different types of luteal phase support in natural cycle frozen embryo transfer (FET) and its effect on pregnancy rates

The ability to transfer frozen embryos makes it possible to keep frozen the amount of embryos created in in-vitro-fertilization (IVF) treatments for later use. Advantages of frozen embryos transfer (FET) include reduced embryo loss after IVF and a higher pregnancy rate. The rate of frozen embryos transfer has increased in recent years due to a higher tendency of single embryo transfer (SET), use of preimplantation genetic testing, and prevention of ovarian hyperstimulation (1,2). Due to developments of freezing technology and techniques in recent years, embryo freezing enables the advantages mentioned above without compromising the pregnancy rate (3).

There are different methods to prepare the endometrium for FET:

1. Natural cycle (NC) - Timing of ovulation by diagnosing the luteinizing hormone (LH) Surge. The advantage of a NC is the natural preparation of the body for implantation without the need for medicinal intervention. The disadvantage is need of intense monitoring to detect ovulation and inflexibility of day of embryo transfer. As a result, NC results in higher percentages of cycle cancellation.
2. Modified natural cycle (mNC) - Inducing ovulation by administration of Human Chorionic Gonadotropin (HCG) trigger. The advantage of ovulation induction with HCG is greater flexibility and ability to plan transfer day according to the availability of the system, with fewer visits by the patient.
3. Medical - preparation of endometrium with estrogen and progesterone. This method is suitable for women who do not ovulate regularly. This allows flexibility of the treatment with fewer cycle cancellations.

Studies that compared pregnancy outcomes of natural versus adapted NC are inconclusive (4-8). In recent years, several studies showed higher clinical pregnancy and ongoing pregnancy rates in NC group compared to group treated with HCG for ovulation induction (7-8).

Recently, several studies showed advantages of FET in NCs. A study published in April 2020 by XITONG LIU in Fertility and Sterility showed a higher rate of live births

and a reduced rate of miscarriages in NC FET group compared to the drug-treated group (9). Additional studies showed higher rates of gestational hypertension (10 - 11), macrosomia and post-term pregnancies in the medicated FET groups (10).

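### Implantation is counted per embryo but women are randomised, so an embryo-level chi-square gives too small a P value if some women receive two embryos with positively correlated outcomes

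*Combined protocol and SAP*

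**What the plan says.** Four statements bear on this point.

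- Unit of randomisation (Study methods): "The distribution of the patients to the two study groups will be done randomly by computer in a ratio of 1:1".
- Outcome (Secondary outcomes): implantation rate is "number of gestational sacs divided by number of embryos transferred". It is the only listed outcome with embryos in the denominator. The others are per transfer or per positive pregnancy test.
- Embryos per woman (Study methods): "The number of embryos that will be returned will be determined according to the age of the woman", and also according to cycle number and embryo quality under the unit's policy. Nothing restricts transfers to a single embryo, and no distribution is given.
- Tests (Statistical calculations): "Comparison of categorical variables will be carried out using the CHI-SQUARE TEST". For continuous variables, "Comparison of continuous variables will be performed using the Students t-Test" or Mann-Whitney. In addition, "A multivariate regression will also be conducted in order to determine which variables are significantly and independently related", with no outcome, unit or clustering term named.

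The plan nowhere says which of these tests applies to implantation, and it does not mention dependence between embryos in the same woman.

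**The concern.** A pooled sacs-over-embryos proportion looks like categorical data, and chi-square is the only test named for categorical data. Applied to embryos, that test takes each one as an independent observation. Two embryos transferred together share the woman and her assigned treatment, so they may tend to succeed or fail together. If they do, the standard error is too small and a significant implantation result could partly be an artefact of the counting unit.

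The outcome is likely to be read. The introduction supports GnRH agonist use partly with a trial in which it "increased clinical pregnancy and implantation rates when frozen cleavage stage embryos were transferred", and the P<0.05 rule is applied without separating primary from secondary outcomes.

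**Working it through.** **The plan's own figure.** For the primary outcome, 32% against 55%, two-sided alpha 5%, power 80%, pooled variance without continuity correction:

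n = [1.960·√(2·0.435·0.565) + 0.8416·√(0.32·0.68 + 0.55·0.45)]² / 0.23² = 71.7, so 72 per arm and 144 in total.

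The stated size reproduces. It is a count of women, and the present point does not touch it.

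**Inputs.** From the documents: 72 women per arm, 1:1 allocation, threshold 0.05. Assumed: the share d of women with two embryos (the rest have one), the within-woman correlation rho, and the same per-embryo implantation probability p in single and double transfers.

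**Design effect.** The mean number of embryos per woman is 1+d. The variance of sacs per woman about p times her embryo count is p(1−p)[(1−d) + 2d(1+rho)]. The embryo-level chi-square uses p(1−p)(1+d). The ratio is

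deff = 1 + 2d·rho/(1+d).

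**Consequences.** Type I error = 2[1 − Φ(1.96/√deff)]. A chi-square P of 0.04 (z = 2.054) becomes 2[1 − Φ(2.054/√deff)].

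| d | rho | deff | Type I error | P of 0.04 becomes |
|---|---|---|---|---|
| 0, or any d with rho=0 | – | 1 | 5.0% | 0.040 |
| 10% | 0.1 | 1.018 | 5.2% | 0.042 |
| 10% | 0.5 | 1.091 | 6.1% | 0.049 |
| 25% | 0.3 | 1.120 | 6.4% | 0.052 |
| 50% | 0.3 | 1.200 | 7.4% | 0.061 |
| 75% | 0.1 | 1.086 | 6.0% | 0.049 |
| 75% | 0.5 | 1.429 | 10.1% | 0.086 |

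**Example.** With d=50% there are 72 × 1.5 = 108 embryos per arm. Suppose 30 against 44 sacs. The chi-square gives P=0.045. Allowing for clustering, P is 0.052 at rho=0.1, 0.067 at rho=0.3 and 0.082 at rho=0.5.

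**Simulation check.** 200,000 null trials per cell, 72 women per arm, P(both implant) = p² + rho·p(1−p). Sizes are for p=25% / 35%.

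| d, rho | Embryo-level chi-square | Cluster-robust | Per-woman t-test |
|---|---|---|---|
| 10%, 0.5 | 6.1 / 6.1% | 5.1 / 5.1% | 5.0 / 5.0% |
| 50%, 0 | 5.1 / 5.2% | 5.1 / 5.2% | 5.1 / 5.1% |
| 50%, 0.3 | 7.5 / 7.5% | 5.1 / 5.1% | 5.1 / 5.1% |
| 75%, 0.5 | 10.3 / 10.2% | 5.1 / 5.0% | 5.1 / 5.0% |

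The formula and the simulation agree to within about 0.2 percentage points, and both alternatives stay close to 5%. Smaller runs at p=30% gave 4.8% (d=50%, rho=0.3) and 4.5% (d=75%, rho=0.5) for Mann-Whitney on per-woman proportions (6,000 trials each). GEE with robust errors gave 5.3% at d=50%, rho=0.3 (1,500 trials).

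**The case against.** The strongest reply is that the plan never assigns chi-square to implantation. A per-woman proportion compared with the t-test or Mann-Whitney is open to the investigators and holds its size. That is true. But the plan does not choose, and the embryo-level chi-square is the more natural reading. If the unit stays open, it can also be chosen after the data are seen.

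The second reply is that inflation needs both double transfers and positive correlation, and the documents establish the frequency of neither. The introduction notes a trend towards single transfer. At d=10% with rho up to 0.5, or at rho=0.1 with d up to 75%, a P of 0.04 stays below 0.05. If rho were negative the test would be slightly conservative (4.2% at rho=−0.1, d=50%). All of this stands and limits the size of the problem. A cluster-robust analysis gives valid inference for either sign.

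Third, the model assumes equal implantation rates in single and double transfers, although the plan ties embryo number to age and embryo quality. With assumed rates of 40% and 20%, d=50% and rho=0 within pairs, deff is 0.2978/0.2933 = 1.015 and the size is 5.2%. So the statement that there is no error at rho=0 is exact only with equal rates, but the departure is small.

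Fourth, live birth rate might raise a similar question if twins are counted twice. That is a separate matter of definition and does not weaken this point.

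Lastly, this is a secondary outcome, and the cited implantation finding compared GnRH agonist plus HCG with HCG alone, not with progesterone. Both facts hold and argue for a modest grade.

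**Conclusion.** The concern holds. On its plain reading the plan would test implantation with embryos as independent units while women are randomised. The resulting P value is too small whenever double transfers and positive within-woman correlation occur together. Over the assumed range of d=10–75% and rho=0.1–0.5, the true type I error runs from 5.2% to 10.1% instead of 5%. The effect may be negligible or material, depending on the unit's transfer practice, which the documents do not describe.

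This concerns one secondary outcome. The sample size is untouched, and so is the primary outcome as long as each woman contributes one transfer. The change should be made because it is cheap, but the trial's main conclusion does not depend on it. Confidence is medium, because d, rho and p are all assumed.

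**What to change.** Add one or two sentences to Statistical calculations that name a single analysis of implantation. There are two sound options:

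1. GEE, or logistic regression with standard errors clustered by woman. This keeps the sacs-over-embryos definition and is the closer match to the stated outcome.
2. A per-woman implantation proportion compared with the t-test or Mann-Whitney already in the plan. This weights each woman equally and so estimates a different quantity when rates differ by embryo number. In the 40%/20% illustration the per-woman mean is 30%, against a pooled rate of 26.7%.

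Under either option, report the number of embryos transferred by arm.

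The data are already needed for the outcome's denominator, so the cost is wording and some interval width. Relative to the embryo-level interval, option 1 widens it by √deff − 1: about 1–4% at d=10% and 2–20% over d=25–75% (rho=0.1–0.5), and not at all if every transfer is single. Option 2 widens it by √[(1−d+d(1+rho)/2)(1+d)] − 1: about 5–19% over d=25–75% and rho=0.1–0.5, and 5–6% over that range of d even at rho=0. No change to sample size, treatment or visits is needed.
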